10.1 VISIT SCHEDULE

10.1.1 Screening Visit (Visit 1-Step1 and Step 2) Week -3 to Week -2

The screening will be done electronically in 2 steps:

- Step 1: electronic informed consent: patients will have been guided to the eConsent web portal by the sites or by multi-channel digital recruiters. The study will be presented to them before eConsent.
- Step 2: eligibility assessment: verification of patient identity, vital signs measurement, and blood draw for central laboratory tests will be done in-person by a Homecare health professional visit. This visit can occur at the patient's home, at work, or at any location providing the adequate space and level of privacy. Investigators will complete the determination of eligibility at the end of screening.

For a complete list of procedures scheduled for each study step please refer to the study flow chart ([Section 1.2](#)).

Demographic data and electronic **informed consent** must be obtained from the patient prior to any study-specific procedures. During the stepwise process on the study web portal for the e-consent, the patient will receive information concerning the aims and methods of the study, its constraints and risks and the study duration and will be provided with the written information. This will be done virtually through the study web portal through video conferencing with the investigator or designee, with the support of animations or text. The informed consent will be counter-eSigned by the investigator. Interactive response technology will be contacted for notification of screening and patient number allocation ([Section 8.4](#)). Please note that it is important to have the IRT contact before any blood sample is drawn because the patient number is given by IRT and it must be reported on the laboratory requisition forms. Homecare visit will be scheduled with the patient.

The following will be collected and assessed by the investigator and the site virtual team (designee and study coordinators):

- Collection of **diabetes history** will include documentation of duration of diabetes, history of microvascular [eye, kidney] and of neuropathic complications and their treatments. For patients with a documented medical history of proliferative retinopathy or macular edema, if the latest ophthalmologic investigation have been performed longer than 12 months prior to the planned randomization, the patient has to be referred to an ophthalmologist (or optometrist) prior to randomization. The previous experience with hypoglycemia during the past 12 months will be verified with the source document.

- **Medical/surgical history** may include macrovascular complications (heart, brain, legs) as well as all additional comorbidities. Alcohol and smoking habits are to be recorded.
- Check of **concomitant medication** refers to documentation of medication including over-the-counter medication taken/administered within the previous 3 months prior to this visit.
- Basal insulin analogs and mealtime insulin doses have to be recorded.
- Further discussion about the study and answering patient questions may occur between the investigator and patients via e-chat.

The following will be performed by the Homecare health professional:

- Verification of patient identity in person
- Determination of the **reference arm for blood pressure (BP)** measurements: after the patient has rested comfortably for at least 10 minutes, BP will be measured on both of the patient's arms while the patient is in sitting position and then again on both arms after 2 minutes. The arm with the higher diastolic BP will be determined at this visit, identifying the reference arm for future measurements. The reference arm will be used for later BP measurements by **the patients themselves** in the virtual group or by the site staff for the traditional group. The average value of the 2 measurements (2 minutes apart) will be recorded in the e-CRF (all BP values are to be recorded in the source data).
- **Heart rate** will be measured at the time of the BP measurement.
- **Height** will be measured when patient's shoes are off, feet together, and arms by the sides. Heels, buttocks, and upper back should also be in contact with the wall when the measurement is made.
- **Body weight** should be obtained with the patient wearing undergarments or very light clothing and no shoes, and with an empty bladder. The floor surface on which the scale rests must be hard and should not be carpeted or covered with other soft material. The same scale should be used throughout the study, and calibrated on a regular basis as recommended by the manufacturer. The weight is read and recorded in the e-CRF and source data.
- Blood will be drawn for all central **laboratory tests** needed for evaluation of the eligibility criteria (eg, HbA1c) of the patients. Patient has to provide a urine sample.
- In WOCBP, the **contraceptive methods**, if used, have to be documented. According to CPMP/ICH/286/95 (20), "Highly effective methods of birth control are defined as those, alone or in combination, that result in a low failure rate (ie, less than 1% per year) when used consistently and correctly." Refer to [Appendix A](#) for details. A serum pregnancy test will be performed.
- If needed, diet and lifestyle counseling should be provided.

At Visit 1-Step 2, the investigator will complete the eligibility assessment of the patients when the laboratory results become available.

As soon as a patient is found ineligible, the patient must not enter the randomized treatment phase and IRT has to be contacted in order to register the patient as a screening failure.

Patients can be rescreened one time before randomization in case of nonevaluable exclusion criteria (eg, not evaluable screening laboratory findings) or in case of manageable exclusion as deemed by the investigator. Rescreened patients will be subject to the screening visit procedures/assessments (see below) including new informed consent signed and allocation of a new patient number.

10.1.2 Randomization Visit (Visit 2)

10.1.2.1 Visit 2-Step 1 (Week -1)

Visit 2-Step 1 telephone call will occur about 1 week after Visit 1-Step 2 when the investigator has received laboratory reports for the screened patients in order to assess exclusion criteria [E 03](#) and [E 12 \(Section 7.2\)](#). The eligible patients will be randomized to the study group through IRT.

Appropriate study materials will be shipped to eligible patients: Bluetooth blood glucose meter with associated accessories (lancets, control solutions, test strips etc.), e-diaries features, and instructions. Bluetooth devices (pulse oximeter, BP cuff, and scale) will be shipped to patients allocated to the virtual group. Bluetooth devices are listed in Appendix E.

Patients of the virtual group will record any symptoms in the eDiary so that the investigator is informed through the study website portal and will record the AE into the e-CRF.

An onsite visit will be scheduled within a week (+/- 4 days) for the traditional group.

Patient randomized in the virtual group will also be scheduled for an onsite visit, but for physical examination only. The virtual Visit 2-Step 2 visit will be scheduled within 1 week (+/- 4 days) of the Visit 2-Step 1 for the virtual group.

Patients should be reminded to perform at least one day of 7-point SMPG prior to the Visit 2-Step 2 visit. Patients of the traditional group will be reminded to bring the glucose meter to the study visit.

10.1.2.2 Visit 2-Step 2 (Week 0)

This is the baseline visit (onsite visit for the traditional group and mixed onsite-virtual visit for the virtual group). The full list of assessments is provided in the study flow chart ([Section 1.2](#)). Additional details are provided below for a number of assessments.

For the traditional group:

- During the week prior to the scheduled site visit:
 - patients should perform at least one day of 7-point SMPG
 - The baseline questionnaires (DTSQs, DDS, HFS, WPAI-SP, OSEP part 1, RUQ, and OSES part 1 resource requirements) should be administered by patient via parallel 6 portal
- Patients will bring the glucose meter to the site and SMPG data will be collected.

- Any AE/SAE, including hypoglycemia, that occurred since Visit 1 will be documented.
- A disease-focused initial physical examination will be performed by the investigators at the study site, including neck palpation of thyroid, screening for diabetic neuropathy (eg, assessment of appearance of feet and ankles, reflexes, and vibration perception at the great toes) and a check for injection site reactions.
- The IMP, Toujeo basal insulin, will be dispensed. The first dose of IMP may start on the day of this visit (ie, evening dosing) or the second day (ie, morning dosing). Patients will document the dose and date/time in the eDiary.

For the virtual group:

- Patients will receive the Bluetooth devices by mail and IMP by DTP before Visit 2-Step 2. Upon receipt, they will activate the devices (Bluetooth, e-diary, digital BP and pulse device, etc) and confirm to the study site the successful connection with the virtual platform.
- They will be scheduled within a week to visit study site in-person for the investigator to perform the physical examination. No other assessments will be done at this onsite visit.
- Patients will be guided for using the device to measure BP, heart rate, and weight appropriately.
- The 7-point SMPG will be performed for at least 1 day within the week prior to the first dose of the IMP and the data will be immediately available via the Bluetooth for investigator's review.
- Any AE/SAE, including hypoglycemia, that occurred since Visit 1 will be documented in the eDiary.
- Baseline PROs should be completed electronically independently from influence of the investigator and the site staff.
- After all baseline assessments have been completed, the investigator will instruct patients to initiate the first dose of the IMP, Toujeo basal insulin, and patients will document the dose and date/time in the eDiary.

All patients in both study groups will be reminded by the study staff to refer to the instructions for use to properly use the Toujeo pens. IMP administration will be explained to patients including reminding the IMP dose, time of the once daily administration, and dose titration requirements ([Section 8.1](#)).

The day of the first administration of IMP will be defined as Day 1.

All patients are asked to self-titrate their IMP according to the algorithm provided ([Section 8.1](#)). The short-acting insulin analog will be continued for mealtime insulin requirements and correction of SMPG according to recommendation ([Section 8.2.1](#)). Investigators and their study staff are required to offer adequate training, thus enabling patients to successfully self-titrate their insulins.

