9.2.3 Patient care endpoints

9.2.3.1 Investigator questionnaires

Site investigators (one per site) will be asked to complete the Overall Study Experience-sites (OSES) questionnaire. The OSES has 2 parts:

- OSES part 1 contains 1 item to examine resource requirements: “Approximately how much time did you spend with this participant (in person or via phone) during this scheduled visit/communication?”. OSES part 1 will be administered following each study visit.
- OSES part 2 contains 2 items to examine relationship (“I had a good relationship with this patient during the study”) and satisfaction with care (“I am satisfied with the level of care I have provided for this participant in this study”). OSES part 2 will be administered at Week 24 (Visit 12) only.

Each item is scored separately.

See questionnaire in [Appendix D](#).

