10.1.4 Onsite/virtual visits (V6, 8, and V10) during treatment period

Three study visits will occur onsite before the EOT for the traditional approach group. Virtual approach group patients will have the corresponding visit as virtual visit.

During these visits, study material (eg, ancillaries and glucose meter accessories) and IMP will be dispensed or shipped, and the patients' progress, SMPG patterns, dose regimens and data collected during the study (eg, hypoglycemia, AE/SAE, average fasting and postprandial SMPGs over the past days) will be discussed. For patients of the traditional group, the IMP dispensation will be done on site by the investigator or pharmacist. For patients of the virtual group, the IMP will be shipped using the DTP service described in [Section 8.1.3](#).

Patients of the traditional group will bring their glucose meter and IMP boxes to the study site at each onsite visit. For patients of the virtual group, the used and unused IMP will be returned to the sites by Marken driver.

Patients of the virtual group will perform all assessments via virtual device for vital signs (BP, HR) and weight measurements.

The investigators and study staff will check and document in the source data if the patient has reached the titration goal or not at each visit. Appropriate titration will be continued until target fasting SMPG without hypoglycemia has been reached.

Investigational medicinal product compliance (collecting and counting used and unused cartridges and syringes) will be checked and addressed with the patients. The IMP compliance will be checked by video chat between the patients of the virtual approach group and the site staff.

Consultation for diet and life-style modification should be provided during the visits if needed.

Overall Study Experience-Sites part 1 questionnaire (resource requirement) should be completed by the Investigator.

Within 1 week prior to Visit 10, patients should be reminded, if needed, to perform at least one day of 7-point SMPG.

Resource use questionnaire will be completed by the patients at Visits 6, 8, and 10.

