11.4.3.3.1 Analysis of investigator questionnaires

For OSES ([Section 9.2.3.1](#)) a descriptive summary will be provided for each approach group at each applicable visit.

For OSES part 1 (study-specific resource requirements), a descriptive summary will be provided for each approach group at each applicable visit, and a total time will be calculated for each patient and averaged within each approach group. Overall Study Experience-Sites part 1 scores will be compared between approach groups using an ANCOVA. This model will include fixed categorical effects of approach group, on randomization strata of screening HbA1c ($<7.6\%$, $\geq 7.6\%$) and randomization strata of sites as well as continuous fixed covariates of corresponding baseline score.

For OSES part 2 (relationship and satisfaction), a descriptive summary will be provided for each item for each approach group at Week 24. Item scores will be compared between approach groups using an ANOVA. This model will include fixed categorical effects of approach group, on randomization strata of screening HbA1c ($<7.6\%$, $\geq 7.6\%$) and randomization strata of sites.

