2.1.8 Investigator (clinician) reported outcome (ClinRO) endpoints

Overall Study Experience-sites (OSES) questionnaire

Site investigators (one per site) will be asked to complete the Overall Study Experience-sites (OSES) questionnaire. The OSES has 2 parts:

- OSES Part 1 contains 1 item to examine resource requirements: "Approximately how much time did you spend with this participant (in person or via phone) during this scheduled visit/communication?". OSES Part 1 will be administered following each study visit.
- OSES Part 2 contains 2 items to examine relationship ("I had a good relationship with this patient during the study") and satisfaction with care ("I am satisfied with the level of care I have provided for this participant in this study"). OSES Part 2 will be administered at Week 24 (Visit 12) only.

Each item is scored separately.

See questionnaire in [Appendix K](#).

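### Protocol 10.1.2.2 has traditional-group patients complete OSES Part 1, an investigator item on time spent at a visit, before the baseline visit takes place; flow chart footnote o adds to the conflict over who completes it

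*Protocol*

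**What the plan says.** For the traditional group at Visit 2-Step 2 (Week 0), Protocol 10.1.2.2 sets the timing as "During the week prior to the scheduled site visit", and its list of baseline questionnaires ends "RUQ, and OSES part 1 resource requirements) should be administered by patient via parallel 6 portal". The virtual-group instructions in the same section refer only to baseline PROs and do not name OSES.

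Elsewhere OSES is a site instrument. Protocol 9.2.3.1 states: "Site investigators (one per site) will be asked to complete the Overall Study Experience-sites (OSES) questionnaire". The one item in Part 1 is "Approximately how much time did you spend with this participant (in person or via phone) during this scheduled visit/communication", and "OSES part 1 will be administered following each study visit". SAP 2.1.8 classes OSES as clinician-reported and repeats the timing: "OSES Part 1 will be administered following each study visit". For Visits 6, 8 and 10, Protocol 10.1.4 says "Overall Study Experience-Sites part 1 questionnaire (resource requirement) should be completed by the Investigator". Section 10.1.5 gives it to the investigator at Visit 12 as well.

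Footnote o of the flow chart (Protocol 1.2, repeated in SAP Appendix B) hangs on the heading that covers both the patient questionnaires and the two OSES rows. It has the virtual group's questionnaires done remotely at home, and the traditional group's done electronically before the baseline site visit.

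On analysis, Protocol 11.4.3.3.1 plans a summary at each visit, states that "a total time will be calculated for each patient and averaged within each approach group", and compares the groups with the baseline score as covariate. SAP 2.4.7.6 keeps that covariate in a repeated-measures model.

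**The concern.** The item asks the investigator how long a particular visit took. A patient answering through a portal some days beforehand is the wrong respondent and cannot know the answer. If a site follows 10.1.2.2 as written, the Week 0 value for that patient does not measure site time.

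Site resource requirement is a named secondary endpoint, and the burden on sites is part of the rationale for testing a virtual approach. For the traditional group, Visit 2-Step 2 is an on-site visit with a physical examination and dispensing of study drug. For the virtual group it combines an on-site examination with a video contact. It is therefore a visit at which site time is of real interest. The visit schedule and the flow chart are the parts of a protocol that sites work from, and here both point away from the definition in 9.2.3.1.

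**Working it through.** The plan states no figure on this point. The check is a comparison of passages, followed by a count.

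**Who completes OSES Part 1, and when**

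| Place | Respondent | Timing |
|---|---|---|
| Protocol 9.2.3.1; SAP 2.1.8 | Site investigator | After each visit |
| Protocol 10.1.2.2, traditional group | Patient, by portal | Week before Visit 2-Step 2 |
| Protocol 10.1.2.2, virtual group | Not stated | Not stated |
| Flow chart footnote o, traditional group | Not stated | Before the baseline site visit |
| Flow chart footnote o, virtual group | Patient, by implication (at home) | Not stated |
| Protocol 10.1.4 (Visits 6, 8, 10) | Investigator | At these visits |
| Protocol 10.1.5 (Visit 12) | Investigator | At this visit |

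Rows 1 and 2 cannot both be followed. Footnote o repeats the pre-visit timing for the traditional group. For the virtual group it leaves the respondent unclear, and nothing in 10.1.2.2 settles that.

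**How many entries**

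The flow chart schedules OSES Part 1 at Visit 2-Step 2 and Visits 3 to 12: 1 + 10 = 11 entries per patient. The affected entry is 1/11 = 9% of them. It also belongs to 1 of the traditional group's 5 on-site visits (Visits 2-Step 2, 6, 8, 10 and 12).

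SAP section 2 reports 15 patients randomized. At one Visit 2-Step 2 entry each, at most 15 are in question: those of the traditional patients under 10.1.2.2, and those of both groups if footnote o is read literally.

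**Which outputs use the entry**

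- Summary by visit (Protocol 11.4.3.3.1): yes, at baseline.
- Covariate in the planned comparison (Protocol 11.4.3.3.1, SAP 2.4.7.6): yes.
- Total time per patient (Protocol 11.4.3.3.1): not stated whether Visit 2-Step 2 counts. The Synopsis describes the endpoint as covering the 24-week treatment period.
- On-treatment average (SAP 2.5.2): no. It uses post-baseline completions.

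**Whether the SAP would catch a wrong entry**

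SAP 2.5.4 handles PRO and ClinRO data together, assigns them to visits by date, and states no check of the respondent. The Day 1 window for OSES Part 1 in Table 2 is study day -28 to 1, counted from first study-drug injection, so an entry made in the week before the visit is accepted. The next window opens on day 5, so an investigator entry made on days 2 to 4 falls in none.

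**The case against.** The strongest reply is that this is a drafting slip and that the right instruction prevails. The definition in both documents, the sections for Visits 6, 8, 10 and 12, and the ClinRO label all point to the investigator, and the item is plainly addressed to site staff. A site that followed 9.2.3.1 holds a valid entry. This stands: the text shows a contradiction, not that any value was wrongly collected. The OSES form is not visible in the public copy, so the portal assignment cannot be checked.

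A reader might infer three stronger things that the documents do not support.

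- **One-sided bias between the groups**, with a patient's guess in one arm set against an investigator's record in the other. Only the traditional group is explicitly misassigned in 10.1.2.2. But footnote o makes the virtual-group respondent unclear, and no baseline instruction for that group names the investigator.
- **A large share of total site time.** Assuming 30 minutes for each of four later site visits and 15 for each of six calls, a baseline visit of 45, 60 or 90 minutes would be 45/255 = 18%, 60/270 = 22% or 90/300 = 30% of the total. No visit lengths appear in the documents, inclusion of baseline in the total is not stated, and a visit's share of the total is not the size of an error.
- **A faulty SAP window.** The day -28 to 1 window is common to the baseline questionnaires. First injection may fall on the day after the traditional group's visit, so a correct investigator entry can also precede Day 1. The window does not create the problem; it only fails to detect it.

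**Conclusion.** The contradiction is real, and it concerns an operational instruction. Where 10.1.2.2 is followed, the traditional-group Visit 2-Step 2 entry for OSES Part 1 comes from the wrong respondent before the visit. Where footnote o is read literally, the virtual-group entry may also come from the patient.

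The size is limited: 1 of 11 scheduled entries per patient. The opening of SAP section 2 says that the objectives will not be analyzed as planned and that only basic descriptive output will be given for the 15 randomized patients. The covariate problem would have mattered in the planned model, but it largely falls away. What remains exposed is the baseline-visit summary, the listings and, if baseline is counted, the total time.

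This rests on sites having followed the visit section or the flow chart rather than 9.2.3.1, which the documents cannot show either way.

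**What to change.** In the Protocol:

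- Delete OSES Part 1 from the patient-completed list in 10.1.2.2.
- Exclude the OSES rows from footnote o in the flow chart, and likewise in SAP Appendix B.
- State that in both groups the investigator completes OSES Part 1 after Visit 2-Step 2. In the virtual group the entry should cover both the on-site examination and the video contact.

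In the SAP:

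- In Table 2, assign the baseline OSES Part 1 entry by respondent and by the actual Visit 2-Step 2 contact date or dates, instead of by study day -28 to 1. A plain cut-off at the video visit would not do, because it could reject time logged at the virtual group's earlier on-site examination.
- State whether the total time includes Visit 2-Step 2.
- For data already collected, check who made each Visit 2-Step 2 entry and when, and flag any made by a patient or before the visit.

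The cost is a short text clarification, a portal form assignment, one SAP rule and a check of at most 15 entries. No new procedure or visit is needed.
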